3.4.2 Secondary Endpoints Analysis

The secondary objectives are to determine whether the combination of SL BUP/NAL SOC background therapy and the digital therapeutic OXD01 is superior to SL BUP/NAL alone with respect to the following variables. Note that the secondary objectives are listed in priority order for potential gatekeeping statistical approaches. The second test will only be conducted if the first test is statistically significant, and the following tests will only be conducted if the previous test is statistically significant.

The following secondary endpoints will be tested in a hierarchical fashion to protect the family-wise type I error:

- Cumulative response – The cumulative response rate from Week 6 to Week 25 of treatment. Response is defined as the presence of both a negative urine drug test for opioids and a self-report negative for illicit use of opioids at a study visit.

To compare the two treatment groups with respect to their cumulative distribution functions of the proportion of subjects responding, the Kolmogorov-Smirnov methodology will be used.

- Illicit use of opioids - The cumulative response rate from Week 6 to Week 25 of treatment with respect to the percentage of urine drug tests negative for opioids will be the primary metric for this variable. To compare the two treatment groups with respect to their cumulative distribution functions of the proportion of subjects responding, the Kolmogorov-Smirnov methodology will be used.
- Self-reports of illicit use of opioids - The cumulative response rate from Week 6 to Week 25 of treatment with respect to the percentage of self-reports negative for illicit use of opioids will be the primary metric for this variable. To compare the two treatment groups with respect to their cumulative distribution functions of the proportion of subjects responding with self-reports negative for illicit opioid use, the Kolmogorov- Smirnov methodology will be used.
- Percentage of subjects abstinent - Abstinence is defined as a subject having urine drug tests negative for opioids as well as self-reports negative for illicit use of opioids at Week

25. Each subject will be scored as abstinent or non-abstinent and the groups will be compared using a chi-squared test.

- Proportion of subjects completing the study - A completer is defined as a participant who completed either the UDS or the self-report assessment at the Week 25 visit. The groups will be compared with respect to the proportion of completers using a chi-squared test.
- Clinical global impression - This will be evaluated in two ways
 - Score on the CGI-I scale at week 13 and Week 25
 - Change from baseline in the Clinical Global Impression-Severity score at Week 13 and Week 25

CGI scores will be evaluated using General Linear Model (GLM) methodology with treatment as categorical covariate. If substantial deviations from the model assumptions are observed, then supportive analyses such as non-parametric assessments including a Mann-Whitney U test will be performed.

- Opioid cravings - Change from baseline in the opioid craving score using the Opioid Craving VAS from Week 4 to Week 25. Opioid Craving scores will be evaluated using GLM methodology with treatment as categorical covariate. If substantial deviations from the model assumptions are observed, then supportive analyses such as non-parametric assessments including a Mann-Whitney U test will be performed.
- Use of illicit non-opioid drugs of abuse - The cumulative percentage of subjects with urine drug tests negative for illicit drugs of abuse (excluding opioids) plus self-reports negative for illicit drug use for the period from Week 6 to Week 25 will be evaluated using the Kolmogorov-Smirnoff methodology.
- Number of hospitalizations, emergency department visits, and overdoses, and the ability to resume work, school, or other productive activity. descriptive statistics (count and percentage) will be summarized by treatment.

3.4.3 *Exploratory Analysis*

- Percentage of subjects with longer abstinent – Longer abstinence is defined as a subject having urine drug tests negative for opioids as well as self-reports negative for illicit use of opioids at Week 22 – Week 25. Each subject will be scored as abstinent or non-abstinent and the groups will be compared using a chi-squared test.

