#### 11.4 Secondary Objectives

The secondary objectives are to determine whether the combination of SL BUP/NAL SOC background therapy and the digital therapeutic OXD01 is superior to SL BUP/NAL alone with respect to the following variables. Note that the secondary objectives are listed in priority order for potential gatekeeping statistical approaches.

- Cumulative response – The cumulative response rate from Week 6 to Week 25 of treatment. Response is defined as the presence of both a negative urine drug test for opioids and a self-report negative for illicit use of opioids at a study visit.

To compare the two treatment groups with respect to their cumulative distribution functions of the proportion of subjects responding, the Kolmogorov-Smirnoff methodology will be used.

- Illicit use of opioids - The cumulative response rate from Week 6 to Week 25 of treatment with respect to the percentage of urine drug tests negative for opioids will be the primary metric for this variable. To compare the two treatment groups with respect to their cumulative distribution functions of the proportion of subjects responding, the Kolmogorov-Smirnoff methodology will be used.
- Self-reports of illicit use of opioids - The cumulative response rate from Week 6 to Week 25 of treatment with respect to the percentage of self-reports negative for illicit use of opioids will be the primary metric for this variable. To compare the two treatment groups with respect to their cumulative distribution functions of the proportion of subjects responding with self-reports negative for illicit opioid use, the Kolmogorov-Smirnoff methodology will be used.
- Percentage of subjects abstinent - Abstinence is defined as a subject having urine drug tests negative for opioids as well as self-reports negative for illicit use of opioids at Week 25. Each subject will be scored as abstinent or non-abstinent and the groups will be compared using a chi-squared test.
- Proportion of subjects completing the study - A completer is defined as a participant who completed either the UDS or the self-report assessment at the Week 25 visit. The groups will be compared with respect to the proportion of completers using a chi-squared test.
- Clinical global impression - This will be evaluated in two ways.
  - Score on the CGI-I scale at week 12 and Week 25
  - Change from baseline in the Clinical Global Impression-Severity score at Week 12 and Week 25

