3.1.3 Definition of Baseline

Baseline is defined as Study Day 1. Subject with missing baseline value will be considered as missing and will be excluded from the analysis for the change from baseline endpoints.

3.1.4 *Summary Statistics*

In general, categorical data will generally be summarized with counts and percentages of subjects. The denominator used for the percentage calculation will be clearly defined.

Continuous data will generally be summarized with descriptive statistics including n (number of observations), mean, median, standard deviation, minimum, and maximum.

3.1.5 *Hypothesis Testing*

Corresponding with the primary efficacy objective of the study, the primary inference for hypothesis testing is the treatment difference between the combination of SL BUP/NAL SOC background therapy and the digital therapeutic OXD01, and SL BUP/NAL alone to reduce opioid use, as measured by the treatment success rate from Week 6 to Week 25. The hypothesis testing is based on a two-sided test with significance level at 0.05.

3.1.6 *Evaluation of Site Effect*

This is a multicenter study. Sites will not be pooled for any planned inferential analysis.

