3.4 Efficacy Assessment

Efficacy data will be summarized by randomized treatment based on the FA Population. The primary efficacy endpoint will also be summarized based on the mFA Population.

3.4.1 *Primary Endpoints Analysis*

The primary objective of the study is to determine whether the combination of SL BUP/NAL SOC background therapy and the digital therapeutic OXD01 is superior to SL BUP/NAL alone to reduce opioid use, as measured by the treatment success rate. Treatment success is defined as the subject having $\geq 80\%$ of urine drug tests negative for opioids plus $\geq 80\%$ of self-reports negative for illicit opioid use (from the TLFB interview at the same visit) from Week 6 to Week 25. Each subject will be evaluated as a success or failure for this metric and the proportion of subjects in each group demonstrating $\geq 80\%$ of urine drug tests negative for opioids plus negative self-reports for illicit opioid use (from the TLFB interview) will be tested using chi-squared test. Count and percentage of the subjects with treatment success will be summarized by treatment based on FA Population.

If the subject withdrew the study, then the urine drug tests for opioids and self-reports for illicit opioid use after withdrawal will be imputed as positive. If the subject completed the study with any missing visit, then the urine drug tests for opioids and self-reports for illicit opioid use for the missing visit will be imputed as positive.

Sensitivity analysis 1

As supportive analyses to the primary analysis for the primary endpoint, sub-group analysis using a similar chi-squared test as described above will be repeated for the following factors:

- Percentage of subjects meeting primary endpoint by reported compliance rate or who achieved greater than 80% completion of the visits during Week 6 to Week 25
- Subjects who took the dose of buprenorphine versus retention.
 - Target dose or lower: ≤ 16 mg buprenorphine for Suboxone or equivalent formulation; or ≤ 11.4 mg Zubsolv
 - Higher dose than target dose: > 16 mg buprenorphine for Suboxone or equivalent formulation; or > 11.4 mg Zubsolv
- Subjects who received additional behavioral health services

Sensitivity analysis 2

As supportive analyses, the primary endpoint and key secondary endpoints will be performed using the similar statistical methods based on mFA Population.

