5.2 Interim Analysis

No interim analysis is planned for this study.

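### The SAP does not make a significant primary result the condition for entering the secondary hierarchy, so 5% control across primary and secondary endpoints is not secured

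*SAP*

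**What the plan says.** SAP 3.1.5 (Hypothesis Testing) identifies one hypothesis: "the primary inference for hypothesis testing is the treatment difference between the combination of SL BUP/NAL SOC background therapy and the digital therapeutic OXD01", against SL BUP/NAL alone, on the treatment success rate from Week 6 to Week 25. The same paragraph adds: "The hypothesis testing is based on a two-sided test with significance level at 0.05". SAP 3.4.1 says that the success proportions "will be tested using chi-squared test". It does not say what happens to the secondary endpoints if that test fails.

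SAP 3.4.2 repeats a sentence from Protocol 11.4: "Note that the secondary objectives are listed in priority order for potential gatekeeping statistical approaches". It then gives the step rule, "The second test will only be conducted if the first test is statistically significant", and extends it to each later test. Next comes the claim of protection: "The following secondary endpoints will be tested in a hierarchical fashion to protect the family-wise type I error". The list runs in this order:

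1. cumulative response
2. urine tests negative for opioids
3. self-reports negative for illicit opioid use
4. abstinence at Week 25
5. study completion
6. CGI
7. opioid craving
8. non-opioid drug use
9. hospitalizations and related outcomes, which are summarized descriptively

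On the sixth entry the SAP says: "Clinical global impression - This will be evaluated in two ways". These are CGI-I and CGI-S, each at Weeks 13 and 25.

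**The concern.** A hierarchy controls error across the primary and secondary endpoints only if the primary is its first step, or if alpha is divided between the two. Neither is written. The step rule stands in the section on secondary endpoints, and the list it governs contains only secondary endpoints. The plain reading is therefore that the first test is the K-S test of cumulative response, open whatever the primary shows.

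What is at stake is mainly interpretation. A trial that missed its primary could present cumulative response, and endpoints below it, as error-controlled findings. If the rule can be read two ways, the choice between readings could be made after the results are known.

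**Working it through.** **The plan's own figure.** The SAP gives no numeric family-wise error rate, so there is none to reproduce. The sample size in SAP 2.2.4 (12% versus 25%, two-sided 0.05, 90% power, about 200 per arm) does reproduce. The two-proportion formula gives 186 per arm, or 201 with continuity correction. Exact power at 200 per arm is 90.4% for Fisher's exact test and 92.6% for the uncorrected chi-squared test. I therefore use 200 per arm below.

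**Inputs from the documents.**
- Primary: chi-squared test at two-sided 0.05 (SAP 3.1.5, 3.4.1).
- First listed secondary: two-sample K-S test (SAP 3.4.2). Appendix B codes it in PROC NPAR1WAY with EDF and no EXACT statement, which gives the asymptotic p-value.
- Weeks 6 to 25: 25 − 6 + 1 = 20 weekly visits, so the count of negative visits takes 21 values (0 to 20), and 80% is 16 of 20.
- Missing visits are imputed as positive (SAP 3.4.1).
- No alpha is spent elsewhere: "No interim analysis is planned for this study".

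**Bounds, with both entry tests at 0.05.**
- Bonferroni: 0.05 + 0.05 = 0.10.
- Independence: 1 − 0.95² = 0.0975.
- Correlated normal statistics: 1 − P(|Z₁| < 1.96 and |Z₂| < 1.96). The correlation is an assumption; the documents give none.

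| Correlation | P(at least one false positive) |
|---|---|
| 0 | 0.0975 |
| 0.3 | 0.095 |
| 0.5 | 0.091 |
| 0.7 | 0.083 |
| 0.9 | 0.070 |
| 1 | 0.050 |

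**Simulation under the global null.** There were 6,000 trials per scenario. Each subject's rate of negative visits was drawn from a beta distribution, and a visit counted as negative or not as a whole. Dropouts were scored positive from a random visit onward. The dropout rates and beta parameters are assumptions.

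| Dropout | Success rate | Primary rejects | K-S rejects | Both | Either |
|---|---|---|---|---|---|
| 40% | 9.8% | 0.0483 | 0.0157 | 0.0033 | 0.0607 |
| 30% | 6.7% | 0.0472 | 0.0190 | 0.0027 | 0.0635 |
| 50% | 14.3% | 0.0485 | 0.0227 | 0.0050 | 0.0662 |

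Check on the first row: 0.0483 + 0.0157 − 0.0033 = 0.0607. The Monte Carlo standard error is about √(0.063 × 0.937 / 6,000) = 0.003. Two further null simulations under other assumed dropout and variation gave 6.1-6.5% and 6.6-7.0%. The excess over 5% is small because the asymptotic K-S test is conservative on a 21-point outcome: it rejects only about 2% of the time.

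**Secondary endpoints alone.** A fixed sequence with one test per step holds 0.05. The CGI entry has four comparisons and no order or split. If all four nulls are true and the comparisons are independent, that step alone has error 1 − 0.95⁴ = 0.185. Nor is it defined which CGI result would open the craving step.

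**The case against.** The strongest reply is that the SAP never names the first test. SAP 3.1.5 singles out one primary inference, and the step rule precedes the sentence that introduces the secondary list, so a primary-first reading is available. A reader might infer that the SAP deliberately starts at the secondaries and permits claims after a failed primary. The documents do not support that: no sentence permits it. This is an omission, not an explicit rule. It still matters, because a gatekeeping rule has to be unambiguous before results are seen, and *potential* leaves even its use uncertain.

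Second, the family is not defined and no alpha is assigned to the secondary chain. A reader might infer that the claim of protection is simply false. If the family is the secondary endpoints alone, the claim is correct down to the CGI step, and the missing primary gate does not break it. But the SAP does not limit its claim in that way, and many readers would take it as covering primary and secondary claims together.

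Third, larger inflation figures should not lead. A K-S test calibrated for ties gives 7.6-8.7%, but the SAP does not specify that version. The 9.75% figure needs independence, whereas both endpoints use the same urine and self-report results. This objection stands.

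**Conclusion.** The gap is real and its numerical effect is modest. No passage makes entry to the secondary hierarchy depend on the primary, so on the plain wording control at 0.05 across primary and secondary endpoints is not secured. With the K-S test as coded in Appendix B, the chance of a false positive on the primary or the first secondary is about 6-7% rather than 5%. That range rests on assumed dropout and between-subject variation, 200 per arm, and a single negative-or-not result per visit. The limit of about 10% for these two tests needs none of those assumptions. On the narrower reading of the family, 0.05 holds until the CGI step and is not secured there. The consequence that matters more is that the status of secondary results after a failed primary is left to interpretation.

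**What to change.** In SAP 3.4.2:

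- State that the first test in the sequence is the primary endpoint on the FA Population at two-sided 0.05. Cumulative response is tested only if the primary is significant, and each later endpoint only if the one before it is significant, all at two-sided 0.05. Results after the first non-significant step are descriptive.
- Delete *potential*, so that the hierarchy is the plan and not an option.
- Give the four CGI comparisons a fixed order, or adjust within the step (for example 0.05 / 4 = 0.0125 each) and require all four to be significant before moving to craving.

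With these changes, family-wise error across the primary and the tested secondary endpoints is at most 0.05, provided every other step yields a single test. Protocol 11.4 orders the secondaries and leaves the method open, so this does not conflict with it. The sample size and the power of the primary test do not change. The cost is a few sentences in the SAP and the loss of formal secondary claims if the primary fails.

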2.2.2 Randomization

Eligible subjects will be randomized to one of two treatment groups in a 1:1 ratio:

- SL BUP/NAL SOC background therapy
- SL BUP/NAL + OXD01 digital therapy

Eligible subjects will be randomized on Day 1 through an IRT system.

Each subject will be identified by a unique randomization number assigned by the IRS system on Day 1. Prior to randomization, subjects will be identified by a screening number, assigned when the subject signs the ICF.

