2.2.4 Sample Size Determination

Treatment success is defined as the subject having $\geq 80\%$ of urine drug tests negative for opioids plus $\geq 80\%$ of self-reports negative for illicit opioid use (from the TLFB interview at the same visit) from Week 6 to Week 25 of the study. Current literature suggests that the proportion of subjects likely to be successful by this measure while under treatment with the control agent may be approximately 12%. [1] If OXD01 is effective in improving this percentage to 25%, approximately 200 subjects will be required to receive each treatment to provide 90% power to

detect such a difference at an $\alpha = 0.05$ level (Fisher's Exact Test). Approximately 510 opioid dependent males and females will be screened to randomize approximately 400 subjects.

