APPENDIX B: SAS Programming Example

The sample SAS code for Chi-Squared test is included below:

```
PROC FREQ DATA=DATA;  
  TABLES RESPONSE * TREATMENT / CHISQ;  
  RUN;
```

The sample SAS code for Kolmogorov-Smirnov (KS) test is included below:

```
PROC NPAR1WAY DATA=DATA WILCOXON EDF;  
  CLASS TREATMENT;  
  VAR CUMULATIVE_RESPONSE;  
  RUN;
```

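### The sample code gives large-sample Kolmogorov-Smirnov p-values for the lead gatekept secondary endpoints; on a tied 0-to-20 score these are conservative, and an exact or Monte Carlo p-value would recover the lost power

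*SAP*

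**What the plan says.** SAP 3.4.2 tests the secondary endpoints in a fixed order, each step conditional on significance at the step before. The first three are cumulative response, percentage of opioid-negative urine tests and percentage of opioid-negative self-reports. The arms are compared "with respect to their cumulative distribution functions of the proportion of subjects responding, the Kolmogorov-Smirnov methodology will be used". Protocol 11.4 names the same method: "with respect to their cumulative distribution functions of the proportion of subjects responding, the Kolmogorov-Smirnoff methodology will be used". Non-opioid drug use, further down the list, is also tested this way. Abstinence, completion, clinical global impression and craving sit between.

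Neither text says whether the p-value is exact or asymptotic. SAP Appendix B gives sample code, "PROC NPAR1WAY DATA=DATA WILCOXON EDF", with a CLASS and a VAR statement and no EXACT statement. SAP 7 leaves detailed programming specifications to a separate document.

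The rule that missing and post-withdrawal results count as positive is in SAP 3.4.1, under the primary endpoint, and is not repeated in 3.4.2. The test level is in SAP 3.1.5: "The hypothesis testing is based on a two-sided test with significance level at 0.05". It is stated for the primary comparison, and no other level is given for the secondary tests.

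**The concern.** The large-sample Kolmogorov-Smirnov reference distribution assumes continuous data. With many tied scores it overstates the p-value, so the test rejects less often than its nominal level. Cumulative response is the first gate and the next two gates use the same test, so lost power there can close every later secondary claim, and no extra error protection is needed in return.

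A second, smaller matter is direction. The two-sided statistic is the largest absolute gap between the two distribution functions and carries no sign. The stated objective is superiority of OXD01, yet the hierarchy does not say that the difference must favour OXD01 before the next test opens, and no effect estimate is specified for these endpoints.

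**Working it through.** **Inputs from the documents.** Allocation is 1:1 (SAP 2.2.2: "Eligible subjects will be randomized to one of two treatment groups in a 1:1 ratio"). SAP 2.2.4 gives control success "while under treatment with the control agent may be approximately 12"%, then "If OXD01 is effective in improving this percentage to 25"%, and "approximately 200 subjects will be required to receive each treatment to provide 90% power to" detect this. The level is 0.05, two-sided. The visit schedule is in SAP 2.2.1.

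**Step 1: the plan's own figure.** With p1 = 0.12, p2 = 0.25 and mean 0.185:

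n = [1.960·√(2·0.185·0.815) + 1.282·√(0.12·0.88 + 0.25·0.75)]² / 0.13² = (1.0763 + 0.6938)² / 0.0169 ≈ 185.4, so 186 per arm, or 201 with continuity correction.

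Exact enumeration at 200 per arm gives 90.4% power for Fisher's exact test and 92.6% for the uncorrected chi-squared test. The stated 200 per arm and 90% reproduce. They concern the primary endpoint only; the plan gives no power for the Kolmogorov-Smirnov endpoints.

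**Step 2: number of score values.** There are 13 visits for urine screen and interview only (Weeks 6, 8, 10, 12, 14-16, 18-20, 22-24) and 7 evaluation visits (Weeks 7, 9, 11, 13, 17, 21, 25). 13 + 7 = 20. If missing counts as positive, every denominator is 20 and the score takes at most 21 values.

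**Step 3: critical distance.** The asymptotic test refers D·√(n1·n2/N) to the Kolmogorov limit. Here √(200·200/400) = 10, so the 5% critical D is 1.358/10 = 0.136. A critical value that respects the ties was 0.120 to 0.130 in the simulations of Step 5, with attained size 3.9 to 4.9%.

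**Step 4: true size at nominal 5%.** The documents give no score distribution, so one is assumed: a share of subjects at zero, the rest beta-binomial over 20 visits (precision 2), tuned so that 12% score at least 16 of 20 (80%). This treats the joint score as the success measure. 60,000 simulated trials per row, 200 per arm:

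| Subjects at zero | True size |
|---|---|
| 12 to 44% | 2.0-2.3% |
| 52% | 1.5% |
| 61% | 1.0% |
| 71% | 0.5% |
| 80% | 0.1% |

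Flat or U-shaped scores gave 2.2 to 2.6%. If the percentage used attended visits only, size was 1.4 to 3.3%. With continuous data it was 4.1%, so just under 1 point of the shortfall from 5% is not due to ties.

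**Step 5: power at 200 per arm.** Same model, with both arms tuned to the stated success rates. In the first row there is no separate zero group and precision runs from 0.6 to 2.0.

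| Scenario | Asymptotic K-S | Tie-respecting K-S | Difference (points) | Wilcoxon |
|---|---|---|---|---|
| 12% v 25%, whole distribution shifts | 98.1-99.1% | 99.0-99.7% | 0.5-0.9 | 99.9% |
| 12% v 25%, 20% never respond | 91.1% | 94.5% | 3.4 | 94.6% |
| 30% never respond | 84.5% | 89.7% | 5.2 | 83.8% |
| 40% never respond | 75.9% | 85.8% | 9.9 | 67.1% |
| 50% never respond | 66.2% | 79.5% | 13.3 | 48.8% |
| 60% never respond | 58.4% | 78.3% | 19.9 | 32.9% |
| 12% v 20%, 30% never respond | 43.8% | 53.4% | 9.6 | 51.3% |
| 12% v 20%, 50% never respond | 24.4% | 38.0% | 13.6 | 25.4% |

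As a check on the model, the chi-squared test at 16 of 20 had 92.5 to 92.7% power in the 12% v 25% rows, matching the exact 92.6% in Step 1. Where OXD01 instead moved subjects out of the zero group (61% to 19%, or 66% to 29%), both Kolmogorov-Smirnov versions had 100% power.

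**The case against.** The strongest reply has four parts.

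- **Nothing is invalid.** A conservative test keeps the type I error below 5%, and the primary analysis does not use it. This stands. The cost is power only.
- **The loss may be negligible.** At the design effect it is under 1 point if the whole distribution shifts, and nil if OXD01 empties the zero group. Losses near 10 points or more at 12% versus 25% needed about 40% or more of subjects to be unaffected. This stands, and it is why the size must be given as a range.
- **The text does not say asymptotic.** The inference rests on code labelled as a sample, and further specifications sit elsewhere. This stands in part. It is the only implementation shown, and followed as written it gives the asymptotic p-value.
- **Direction is read from the results anyway.** This is fair for interpretation. A gate is a formal rule, however, and this one is worded only in terms of significance.

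A reader might also infer that the Wilcoxon test, already requested in the sample code, should decide instead. The documents do not support that. Both define the comparison as one of distribution functions, and SAP 6 says the plan does not deviate from the protocol analysis, so the switch would depart from Protocol 11.4. Nor is Wilcoxon uniformly more powerful: in Step 5 it ranges from 99.9% down to 32.9% at 12% versus 25%, and with 30% or more unaffected it falls below even the asymptotic Kolmogorov-Smirnov test.

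**Conclusion.** The point holds as an avoidable loss of power in the secondary hierarchy. Run as the sample code stands, the Kolmogorov-Smirnov tests have a true size of roughly 1 to 2.5% for plausible score distributions. Over everything examined, including attended-visit denominators, the range is 0.1 to 3.3%. At 12% versus 25% the power given up is 0.5 to 0.9 points for a whole-distribution shift and 3.4 to 19.9 points if 20 to 60% of subjects never respond in either arm.

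This rests on three assumptions: the score distributions, which the documents do not give; the large-sample p-value, which follows from the sample code; and missing counted as positive for these endpoints, which SAP 3.4.2 does not state. Without the third, the denominators vary and ties are fewer, but size was still below 5% in every case tried.

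Two stronger readings should be avoided. One is that the true error rate is a known 1 to 2%; it depends on a distribution nobody has specified. The other is that the trial's error control or its primary conclusion is at risk; neither is.

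**What to change.** In SAP 3.4.2 and Appendix B:

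1. Keep Kolmogorov-Smirnov as the deciding test, and take its p-value from an exact or Monte Carlo permutation method, for example by adding `EXACT KS / MC;` with a fixed seed and number of samples.
2. Require the difference to favour OXD01 before the next test opens, judged for example by the sign of the difference in mean percent negative.
3. Report that mean difference with a 95% CI as a supportive estimate.
4. State whether missing counts as positive for these endpoints.
5. Apply the same to the non-opioid drug endpoint.

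The cost is one line of code and a few sentences, with no new data and no departure from the test in Protocol 11.4. The permutation p-value still holds the 5% level, and the direction rule can only make a gate harder to pass. Because the critical distance moves from 0.136 to about 0.120-0.130, a borderline result could change. The trial is open-label, and SAP 3.2.2 already lists exclusions by site, so the change should be dated and made before database lock and before any comparison by arm.
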